### **5.5 Efficacy Measures**

### **5.5.1 Primary Efficacy Measures**

The primary efficacy endpoint is the change from baseline in BUN evaluated at 24 hours following initiation of CRRT with the Prismaflex HF20 Set. BUN is to be measured at the start of CRRT treatment with the Prismaflex System, specifically BUN measurements will be taken no earlier than one hour prior to the start of CRRT and no later than 15 minutes after the start of CRRT. BUN will also be measured at 24 hours after initiation of CRRT. More specifically, BUN will be measured no later than one hour after 24 hours past CRRT initiation (25 hours treatment mark) and no sooner than one hour before 24 hours after CRRT initiation (23 hours mark). Change in baseline of BUN to 24 hours after CRRT initiation will be calculated as a percentage using the following equation:

$$\Delta BUN = \frac{BUN_{0hr} - BUN_{24hr}}{BUN_{0hr}} \times 100\%$$

Where BUNohr is BUN recorded at baseline and BUN24hr is BUN recorded at 24 hours after CRRT initiation.

### 5.5.2 Secondary Efficacy Measures

Creatinine and bicarbonate measurements will be collected according to the same time schedule and assessment windows as given above for BUN and used in a change from baseline analysis calculated as a percentage in the same manner as for BUN.

Change in baseline of creatinine to 24 hours after CRRT initiation will be calculated as a percentage using the following equation:

$$\Delta Cr = \frac{Cr_{0hr} - Cr_{24hr}}{Cr_{0hr}} \times 100\%$$

Where  $Cr_{ohr}$  is creatinine recorded at baseline and  $Cr_{24hr}$  is creatinine recorded at 24 hours after CRRT initiation.

Change in baseline of TCO2 to 24 hours after CRRT initiation will be calculated as a percentage using the following equation:

$$\Delta TCO_2 = \frac{(TCO_2)_{0hr} - (TCO_2)_{24hr}}{(TCO_2)_{0hr}} \times 100\%$$

Where  $(TCO_2)_{0hr}$  is  $TCO_2$ recorded at baseline and  $(TCO_2)_{24hr}$  is  $TCO_2$  recorded at 24 hours after CRRT initiation.

Another secondary endpoint for this study is to analyze the extracorporeal circuit life of the Prismaflex HF20 Set. The clock time of treatment initiation will be recorded along with the clock time of when the patient is taken off of the Prismaflex HF20 Set. The circuit life of the filter will be determined by the duration of time between these two measurements. If the patient has an interruption and is taken off the filter during the first 24 hours of the treatment, the clock time of the treatment interruption start and end will be recorded and subtracted from the total time on the Prismaflex HF20 Set. If the patient has an interruption and is started on a new filter, then the clock time of the CRRT initiation on the new filter will be recorded and this will serve as the start time of the patient's filter.

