2.2 Secondary objectives

The efficacy in removing creatinine and normalizing bicarbonate will be tested in a similar fashion to BUN, both as secondary objectives. Another secondary objective of this study is to evaluate the safety of the Prismaflex System Software Version 7.10 and 7.20 in pediatric AKI patients weighing ≥ 8 and ≤ 20 kg (ie, ≥ 17.6 and ≤ 44.09 lbs). The measurement of the duration of time for which each Prismaflex HF20 Set can be used will be evaluated out to a time period of 72 hours from the initiation of CRRT in each patient.

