Appendix 1 Statistical Plan

Objective

The primary objective of the trial is to verify that the Prismaflex HF20 Set is able to deliver effective treatment in small patients. Its efficacy will be measured by the reduction in blood urea nitrogen (BUN). This will be measured every 12 hours at the start of, and during, treatment. Creatinine reduction and the TCO₂ profile will be assessed as secondary endpoints along with survival time of the Prismaflex HF20 Set out to 72 hours.

. A repeated measures ANOVA will be used to test TCO₂. No formal statistical analysis of the safety endpoint will be carried out; rather these events will be assessed for severity and device-relatedness, and reported in narrative form.

Primary Endpoint

The primary endpoint of analysis will be to demonstrate that a mean reduction of greater than 38% in BUN is seen at 24 hours from initiation of CRRT. This percentage reduction is motivated by the target of getting patients with an initial BUN of 80 mg/dL below 50 mg/dL after 24 hours of treatment.

The null hypothesis to be tested is

*H*₀:
$$\mu \le 38$$
, vs
*H*_a: $\mu > 38$

Where μ stands for the mean percentage reduction in BUN from baseline to 24 hours.

Secondary Endpoints

A secondary endpoint will consist of testing whether there is a significant change in creatinine and TCO_2 from baseline to 24 hours. This will be done by turning the creatinine and TCO_2 readings into percent change from baseline and testing whether the percent change is significantly different from zero for each parameter. Another secondary endpoint is the survival time of the Prismaflex HF20 Set. The failure time of the Prismaflex HF20 Set, defined as when one of the following two alarms continues to

be triggered despite mitigation steps, "Warning: Filter Clotted", and/ or "Caution: TMP Excessive", will be recorded and analyzed to determine the survival function of the filter set. Safety will also be investigated by reporting: AEs, SAEs, device deficiencies and alarms.

In addition, the mean concentrations of BUN, creatinine and TCO₂ will be computed, along with 95% confidence intervals, at baseline and at each subsequent 12-hour sampling time.

Other Measures

Other patient and treatment measures will be captured during each patient's treatment. Summary numbers for these measures (mean, standard deviation, minimum and maximum) will be reported for each time point at which the measure is made.

Statistical Analysis Plan

Analysis of Primary Endpoint

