### 4.2 Secondary Objectives

The secondary objectives of this study are:

- To evaluate the efficacy of removing creatinine and normalizing bicarbonate.
- To evaluate the safety of the Prismaflex System Software Version 7.10 and 7.20 in pediatric AKI patients weighing  $\geq 8$  and  $\leq 20$  kg (ie,  $\geq 17.6$  and  $\leq 44.09$  lbs).
- To determine how long a duration of time each Prismaflex HF20 Set can be used up to a maximum of 72 hours from the initiation of CRRT.

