Continuous data will typically be summarized using the number of patients (n), mean, standard deviation, minimum, median, and maximum, while categorical data will be presented by frequency count and percentage.

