### 12.3 Secondary Analysis

The percent change from baseline to 24 hours after treatment initiation in creatinine and TCO2 will be summarized descriptively.

The survival time of the Prismaflex HF20 Set will be analyzed using a Kaplan Meier survival curve to generate the median (0.50), 1st (0.75) and 3rd (0.25) quartile survival times after the start of CRRT.

The life of a filter that is replaced due to continuous use for 72 hours will be censored for the statistical analysis of this secondary endpoint. Filters that are replaced any time CRRT is stopped for reasons other than the failure to medicate the two alarms specified in Section 5.1 will be censored at their current duration of usage. Only filters that are replaced due to the two alarms (filter clotted, and TMP excessive) shall be considered events for this survival analysis.

Box plots will also be generated to represent the 24 hours percent change in creatinine and TCO2 from baseline.

The secondary analysis will be carried out on the FAS and PPS.

# 

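### The bicarbonate objective is normalization, but its only named efficacy measure is a BUN-style percent reduction in TCO2, which does not show whether a child reached the normal range

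*SAP*

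**What the plan says.** - **Objective.** SAP 4.2: "To evaluate the efficacy of removing creatinine and normalizing bicarbonate". Protocol 2.2: "The efficacy in removing creatinine and normalizing bicarbonate will be tested in a similar fashion to BUN, both as secondary objectives".
- **Endpoint.** Protocol 2.4 names the change from baseline in creatinine and bicarbonate at 24 hours. SAP 5.5.2 makes this "used in a change from baseline analysis calculated as a percentage in the same manner as for BUN", with TCO2 as the bicarbonate measure and the formula (TCO2 at 0 h − TCO2 at 24 h)/TCO2 at 0 h × 100%. A fall is positive and a rise negative.
- **Analysis.** Protocol Appendix 1 planned a test: "testing whether the percent change is significantly different from zero for each parameter". SAP section 11 removes it. SAP 12.3 leaves a descriptive summary and box plots, on FAS and PPS: "The percent change from baseline to 24 hours after treatment initiation in creatinine and" TCO2. SAP section 8 gives the usual statistics: "Continuous data will typically be summarized using the number of patients (n), mean, standard deviation, minimum, median, and maximum".
- **Related output elsewhere.** SAP 13.3 plans, for all laboratory values on the FAS, summaries, change from baseline, and shift tables by low, normal and high. Protocol Appendix 1 plans mean TCO2 with 95% confidence intervals every 12 hours. Protocol 5.8.2.11 records attainment of metabolic control as yes/no, with no criterion.

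None of the related output is named as the measure of the bicarbonate objective.

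**The concern.** BUN and creatinine are meant to fall, so percent reduction suits them. Normalizing bicarbonate means reaching a range, possibly from either side. The formula contains no range, no target and no split by baseline state.

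The inclusion criteria in Protocol 4.2 require AKI by creatinine criteria or fluid overload, not an abnormal bicarbonate. The efficacy summary can therefore mix children who are low, normal and high at baseline. With the test removed, description is all that remains for this objective, so the chosen statistic has to carry the answer.

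**Working it through.** The documents give no planned figure for bicarbonate, no baseline TCO2 distribution and no normal range, so there is no plan figure to reproduce. All TCO2 values below are assumptions in mmol/L. The cohort size of 24 is borrowed from the BUN sample size for illustration only.

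**1. Sign and scale.** With f = (b − e)/b × 100, where b is the 0 h value and e the 24 h value:

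| Move | f |
|---|---|
| 14 → 24 | (14 − 24)/14 = −71.4% |
| 16 → 24 | (16 − 24)/16 = −50.0% |
| 18 → 24 | (18 − 24)/18 = −33.3% |
| 32 → 24 | (32 − 24)/32 = +25.0% |
| 36 → 24 | (36 − 24)/36 = +33.3% |
| unchanged at 24, or unchanged at 16 | 0% |

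Corrections from the two sides have opposite signs. The same 8 mmol/L counts twice as much from 16 as from 32. A value of 0% covers both staying normal and staying acidotic.

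**2. Two cohorts with no high baselines.**

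- Cohort A: 12 stay at 24 and 12 go from 16 to 24. At 24 h, 24 of 24 are normal.
- Cohort B: 12 stay at 16 and 12 go from 16 to 24. At 24 h, 12 of 24 are normal.

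Each yields twelve values of 0% and twelve of −50%:

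- mean = (12 × 0 + 12 × −50)/24 = −25%
- median = (0 − 50)/2 = −25%
- SD = √(24 × 25²/23) = 25.5
- range −50% to 0%

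The box plots are identical, although 100% are normal in A and 50% in B.

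The result does not depend on the value 16. With 18 the shared mean is −33.3/2 = −16.7%; with 14 it is −71.4/2 = −35.7%. Nor does it need an even split. If k of 24 are unchanged, A is always 100% normal and B is (24 − k)/24: 75% for k = 6 and 25% for k = 18.

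**3. Mixed baselines.**

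- 12 children 18 → 24 and 12 children 36 → 24 (all normalized): mean (12 × −33.3 + 12 × 33.3)/24 = 0.0%, SD 34.1.
- 12 children 18 → 12 and 12 children 36 → 48 (all worse): mean 0.0%, SD 34.1, with the same values.

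Taking an assumed endpoint value of 22 to 26, low baselines of 14 to 18 and high baselines of 30 to 38, a fully normalized cohort averages 0% when the share with a high baseline is between 0.35 and 0.87, depending on the values. The documents do not say what the share will be.

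**4. Units alone do not cure this.** In mmol/L, cohorts A and B both give twelve changes of 0 and twelve of +8. The sign becomes natural, but only the baseline category separates the cohorts.

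**The case against.** Much can be said for the plan.

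- **Most of the information is already planned.** A bicarbonate shift table under SAP 13.3 shows how many children low or high at baseline were later normal, and change from baseline is tabulated too. This stands, and it limits the point. But those outputs are safety tables for every analyte, on the FAS only, whereas SAP 12.3 covers FAS and PPS. Nothing ties them to the objective.
- **More than the mean is reported.** A reader might infer that cancellation makes full normalization look like no effect. In general it would not. If 6 children go 16 → 24 and 12 go 32 → 24, the mean is (6 × −50 + 12 × 25)/18 = 0%, but the median is +25%, the range −50% to +25% and the SD √(22,500/17) ≈ 36. No change at all gives an SD of 0. The extra statistics do not, however, separate cohorts A and B.
- **The baseline mix is unknown.** Cancellation needs a sizeable high-baseline group, for which the documents give no evidence. This stands; cohorts A and B do not rely on it.
- **The sign is a label.** A reader might infer that a corrected acidosis would count as failure. It would not: there is no success threshold, no test remains, and the protocol's test was for any difference from zero. What remains is a risk of misreading, since SAP 12.3 speaks of percent change and SAP 12.6 of reduction.
- **Some text is missing.** The exploratory section is absent from the public copy. Only a table title for a bicarbonate analysis of variance and a mention in Appendix 1 of a repeated measures ANOVA for TCO2 remain. Nothing is inferred from them either way.
- **The protocol endpoint is change from baseline.** Replacing it with a responder proportion would depart from Protocol 2.4. This is right, so the remedy should add to the endpoint and not replace it.

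**Conclusion.** The point holds in a limited form. The efficacy measure in SAP 5.5.2 and 12.3 cannot by itself show normalization of bicarbonate, because it ignores where each child started relative to normal. Cohorts with 100% and 50% of children normal at 24 h can produce the same summary and the same box plot. The TCO2 values are assumed, but the ambiguity of 0% follows from the formula and from entry criteria that do not require abnormal bicarbonate.

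The documents do not support the stronger conclusion that the trial cannot answer this objective, or that the bicarbonate results are uninterpretable. The 13.3 shift tables partly answer it. The gap is that no measure of normalization is specified as the efficacy result or planned for the PPS. The primary BUN analysis and the sample size are unaffected.

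**What to change.** Keep change from baseline at 24 hours as the protocol endpoint, and make these changes:

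1. **SAP 12.3:** add the 24 h low/normal/high shift in bicarbonate as the descriptive measure of the bicarbonate objective, on FAS and PPS. Give the number and percentage within the laboratory normal range at 24 h, separately for low, normal and high baseline, with exact 95% confidence intervals. Use the same ranges as the 13.3 shift tables, and state how many children lack a baseline or 24 h value.
2. **SAP 5.5.2 and 12.3:** also present TCO2 change as 24 h minus baseline in mmol/L, so that a rise is positive, and use one label throughout, including in 12.6.
3. **SAP section 11:** record the addition. That section describes its listed changes as agreed with the FDA, so the new line should say whether this one has been.

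The cost is some wording and one table, from data already collected and a classification already planned. No further patients or samples are needed. The downside is small denominators: if 6 of 6 low-baseline children normalize, the exact lower limit is 0.025^(1/6) = 54%, and for 12 of 12 it is 0.025^(1/12) = 74%. Such wide intervals are a fair picture of what up to 30 children can show.

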### **5.6 Safety Measures**

While no formal primary safety analysis is planned for this study, one of the secondary endpoints is the safety of the Prismaflex System in pediatric AKI patients. Adverse Events (AEs) and Serious Adverse Events (SAEs) along with device deficiencies will be continuously collected throughout the study (up to 72 hours after treatment initiation on the final HF20 Set).

The following alarms from Prismaflex System Software Version 7.10 or 7.20 related to fluid balance will be noted and recorded for:

- "Caution: Flow Problem",
- "Caution: Gain Limit Reached",
- "Caution: Loss Limit Reached".

The weight, state of uremia, cardiac status and general physical condition of the patient must be carefully evaluated and recorded by the prescribing physician as required and, at a minimum, each day during treatment.

Fluid overload will also be calculated and reported at baseline and every 12 hours after until treatment completion.

Patient CRRT treatment prescription will be recorded at CRRT initiation and at the beginning of each visit window (every 12 hours) for up to 72 hours. Values recorded will include: CRRT modality, blood prime used, CRRT anticoagulation, blood flow rate, preblood pump flow rate, PBP brand name/manufacturer, PBP formulation, dialysate flow rate, dialysate brand name/manufacturer, dialysate formulation, post filter replacement flow rate, post filter fluid formulation, use of anticoagulation, anticoagulation formulation and anticoagulation rate.

Patient CRRT values will be collected every hour and include: TMP, prescribed patient fluid removal rate, actual period fluid removal, total fluid removal, actual unintended patient fluid gain/loss, prescribed unintended patient fluid gain/loss, and prescribed effluent rate.

Post treatment outcome data will be collected upon the completion of study CRRT and includes: Pediatric Intensive Care Unit (PICU) outcome, total prescribed dose, total delivered dose, dry weight and metabolic control attained and the patient's survival status.

Lab values will be collected at screening and CRRT initiation and will be taken every 12 hours for up to 72 hours after CRRT initiation. Any lab values which are considered abnormal clinically significant will be recorded as an adverse event.

Vital signs will be collected at screening and CRRT initiation and will be taken every hour for up to 72 hours after CRRT initiation. Any vital which is considered abnormal and clinically significant will be recorded as an adverse event.

Heparin anticoagulation use, citrate anticoagulation use and HGB/total calcium monitoring will be observed and recorded throughout the entirety of this study along with any medication taken by the patient.

### 5.7 Pharmacokinetic Parameters

Not applicable.

### 5.8 Completion and Discontinuation

Patients are considered withdrawn from the study if their participation is discontinued before completion of the required evaluations as described in the study protocol. Patients may be withdrawn for any of the following reasons:

- Adverse Event (AE)
- Lack of efficacy
- Non-Compliance with Study Treatment
- Protocol Violation
- Withdrawal of Consent
- Lost to follow-up
- Other (with reason noted)

The investigator may terminate a patient's study participation at any time during the study if he/she judges it to be in the patient's best interest. If a patient is withdrawn from the study, the Clinical Study Manager should be informed at the earliest possible opportunity, regardless of the reason of withdrawal. In addition, a patient may discontinue his or her participation at any time during the study without having to justify their decision. If a patient's participation is discontinued, the reason(s) must be recorded in the source documents and on the electronic case report form (eCRF). If a patient discontinues for any reason, every effort should be made to perform all the procedures that are scheduled for the End of Study Visit. In addition, serious adverse events (SAEs) and adverse device events (ADEs) related or not, will be followed post-study according to the safety plan.

### 6. STUDY POPULATIONS

The study population consists of pediatric patients with Acute Kidney Injury (AKI) treated with continual renal replacement therapy (CRRT). Approximately 30 patients will be enrolled.

### **Inclusion Criteria**

Each patient must meet all of the following criteria to be enrolled in this study.

- 1. Patients with a hospital admission body weight  $\geq$ 8 and  $\leq$ 20 kg (ie,  $\geq$ 17.6 and  $\leq$ 44.09 lbs.)
- 2. Patients with AKI will be defined as either 1) Acute Kidney Injury by the Kidney Disease Improving Global Outcomes (KDIGO) Acute Kidney Injury Guideline serum creatinine criteria, which is a ≥50% rise in serum creatinine over baseline or a 0.3 mg/dL rise in 48 hours, or 2) as AKI as defined by the Pediatric modified Risk, Injury, Failure, Loss, End-Stage Renal Disease (RIFLE) criteria which is a 25% reduction in estimated creatinine clearance, OR 3) a serum creatinine ≥1.2 mg/dL.

OR

Patients with severe fluid overload, defined as a  $\geq 10\%$  Intensive Care Unit (ICU) fluid accumulation (based on ICU admission weight) will be included in the study (% fluid accumulation – [(Fluids in (liters) – Fluid Out (liters)/ICU admit weight (kg) \*100%] and BUN  $\geq 40 \text{mg/dL}$ .

- 3. Patients who have received renal replacement therapy previously can be included in the study if >72 hours have elapsed since previous RRT provision.
- 4. Provide written informed consent form one or both parents as required by the local IRB or a legal guardian unless one parent is deceased, unknown, incompetent or not reasonably available, or when only one parent has legal responsibility for the care and custody of the child per 21 CRF Part 50.55(e).

### **Exclusion Criteria**

Patients who meet any of the following criteria will be excluded from the study.

1. The following hemoglobin exclusion criteria apply:

Weight	Starting HGB (g/dL)	Exclusion Criteria
8.0-20.0 kg	<7.0	Excluded with blood
		prime
8.0-12.0 kg	<8.0	Excluded unless blood
		prime is used
12.1-20.0 kg	<7.5	Excluded unless blood
		prime is used

2. Children who are wards of the state.

### **6.1 Patient Disposition**

A summary will be generated to provide the number and proportion of patients who were screened and who were screen failures (including the reason for screen failure) as well as those patients in the full analysis set (FAS) and per-protocol analysis set (PPS) and those patients who completed the study or prematurely discontinued. A further breakdown will be provided regarding the reasons for premature discontinuation as documented on the patient disposition eCRF. As well as a flowchart of patient disposition will be provided.

### **6.2 Analysis Populations**

The full analysis set (FAS) is based on the intent-to-treat (ITT) principle and includes any patient who received CRRT on the Prismaflex HF20 Set for any period of time.

The Per-Protocol Analysis Set (PPS) is a subset of the FAS including patients who:

- Fulfilled all inclusion criteria
- Did not meet any of the exclusion criteria
- Received at least 20 hours of CRRT treatment on the HF20 Set with no more than 1 interruption which may have included a filter change

- Did not have major protocol deviations that might impact the assessment of the primary endpoint
- Have available measurements for the primary endpoint (BUN) at baseline (within 1 hour prior, and 15 min after initiation of CRRT) and at 24 hours (±1 hour) from start of CRRT

### **6.3 Protocol Deviations**

Protocol deviations will be classified as minor or major deviations (as determined by the Baxter Medical Monitor) and reviewed at a data review meeting.

Subjects with any major protocol deviation that may impact the primary endpoints will be excluded from the per-protocol analysis set, including but not limited to the following:

- Violations inclusion and/or exclusion criteria
- Use of prohibited medication known to influence the primary endpoint
- Improper administration of study product
- Improper assessment of the primary endpoint
- Any other protocol deviations that may impact the primary endpoints

The total number of major and minor protocol deviations and the number of patients having at least one major or minor protocol deviation will be tabulated for each analysis population.

